17 REFERENCES 32

APPENDIX 1. LIST OF ABBREVIATIONS AND ACRONYMS 34

APPENDIX 2. SCHEDULE OF EVENTS FOR EACH STUDY 35

PROTOCOL SYNOPSIS

TITLE	A master protocol to test the impact of discontinuing chronic therapies in people with cystic fibrosis on highly effective CFTR modulator therapy (SIMPLIFY)
NUMBER OF SITES/SUBJECTS	Approximately 80 sites Approximately 920 subjects
STUDY DESIGN	
This master protocol is designed to evaluate the independent effects of discontinuing hypertonic saline (Study A) and dornase alfa (Study B) in people with cystic fibrosis (CF) age 12 and older currently taking the highly effective modulator elxacaftor/tezacaftor/ivacaftor (ETI). Study A and Study B are identical open label two-arm randomized trials consisting of a 2-week screening period, randomization to continue or discontinue hypertonic saline (Study A) or dornase alfa (Study B), followed by a 6-week study period. Subjects taking only hypertonic saline (HS) or dornase alfa at trial entry will be randomized 1:1 to either continue or discontinue the applicable therapy (i.e. HS or dornase alfa). Subjects taking both hypertonic saline and dornase alfa at study entry will be randomized to participate in either Study A or Study B and will be randomized (1:1) to continue or discontinue the applicable therapy (i.e. HS or dornase alfa). After completion of the first study, eligible subjects may subsequently enroll in the alternative study.
 
Clinical outcomes (forced expiratory volume in 1 second [FEV₁], antibiotic use, pulmonary exacerbations, and patient reported outcomes), safety (adverse events) and the subject's perception of how stopping HS or dornase alfa (or both) would impact their daily life will be evaluated in all subjects. Additional outcome measurements will be conducted in a subset of subjects at selected study sites:
 
 • Multiple Breath Washout (MBW) to evaluate changes in lung clearance index (LCI) • Mucociliary Clearance (MCC) using inhaled radio-labeled particles to evaluate changes in mucociliary clearance
STUDY POPULATION	
This master protocol will enroll people with CF who are age 12-17 years old with FEV₁ ≥ 70% predicted, and people with CF who are 18 years and older with FEV₁ ≥ 60% predicted. Subjects must be clinically stable and currently taking ETI in addition to hypertonic saline and/or dornase alfa for at least the 90 days prior to screening. Study A and Study B will enroll approximately 400 subjects each (800 total).
 
After interim safety reviews by the CFF Data Monitoring Committee (DMC), an additional cohort of 120 subjects ≥ 18 years old with FEV₁ between 40 and <60% predicted may be enrolled into Study A (hypertonic saline).

PRIMARY OBJECTIVE	
Study A:
 
 • To determine whether discontinuing hypertonic saline is non-inferior to continuing hypertonic saline among people with CF on ETI, as measured by the 6-week absolute change in FEV₁ % predicted

	
Study B:
 
 To determine whether discontinuing dornase alfa is non-inferior to continuing dornase alfa among subjects on ETI, as measured by the 6-week absolute change in FEV₁ % predicted
PRIMARY ENDPOINT	The absolute change in FEV ₁ % predicted from Visit 1 (randomization) to Visit 3 (week 6)
SAMPLE SIZE	
It is anticipated from prior CF trials conducted through the TDNCC that the attrition and non-adherence rate will be less than 20%, and thus it is reasonable to expect that a total sample size of 400 per study will enable at least 308 subjects to complete the trial and be included in the per-protocol analysis (PPA) population. The PPA population will be the primary analysis population for test of non-inferiority.
 
Assuming a standard deviation for the change in FEV₁% predicted of 8.4, a total sample size of 308 provides 88% power to detect non-inferiority with a margin of -3% absolute FEV₁ % predicted when there is truly no effect of discontinuation.
 
If the DMC approves enrollment of a lower lung function cohort, approximately 60 per arm in Study A will be recruited for exploratory analyses focused on the safety of discontinuation of hypertonic saline in this cohort.

1 BACKGROUND

Health outcomes in people with CF have steadily improved for decades through high quality, multi-disciplinary clinical care models and expanding therapeutic options. These advances have most often been additive and require people with CF and their families to dedicate significant time and resources toward daily care needs. Since 2012, a small but increasing number of people with CF have benefited from highly effective CFTR modulator treatment (HEMT). This “highly effective” description refers to health benefits which are as good as those typically observed in people with a G551D mutation when treated with ivacaftor: sweat chloride reduction by approximately 50 mmol/L, FEV₁ % increase by $\geq 10\%$, large reduction in respiratory symptoms, and $\geq 50\%$ reduction in risk of acute pulmonary exacerbation(1, 2). Until recently, $< 10\%$ of the US CF population has been eligible for HEMT by age and mutation-based label indication. Through continued progress in CFTR modulator drug development and use in younger populations, this number is dramatically increasing and is expected to reach $\geq 90\%$.

As transformative modulator drug therapies emerge, many in the CF Community (patients, families and caregivers) are asking if any of the pre-existing therapies can be reduced or eliminated. A survey of several hundred people with CF, their family members, and CF care providers was conducted in the US in 2018. Survey results from both the CF Community and Clinician-Investigator groups indicate very high support for this research and widespread interest in participating (3). Over 80% of people with CF or their parents surveyed reported that trials testing discontinuation of chronic therapies should be conducted in groups benefitting from HEMT. In parallel, 94% of CF clinicians supported such trials and both groups expressed high interest in participating in trials testing withdrawal of either hypertonic saline or dornase alfa. Both of these nebulized, inhaled therapies were also identified by the CF Community as relatively burdensome components of daily care.

2 STUDY RATIONALE

The initial population of people with CF in the US gaining new access to HEMT in the form of elexacaftor/tezacaftor/ivacaftor (ETI) are age 12 years old and older with at least one F508del mutation. Results from Phase 3 clinical trials (4, 5) testing ETI indicate that this drug combination provides clinical improvements as good as, if not better, than those observed with ivacaftor monotherapy in people with the G551D mutation (2). The SIMPLIFY master protocol will study people treated with ETI who also use inhaled hypertonic saline and/or inhaled dornase alfa by clinical prescription. In this adolescent and adult study population, we will be testing the question of treatment discontinuation rather than the question of whether or not to start a therapy in the first place.

The two lead therapies to be studied in the SIMPLIFY master protocol are hypertonic saline and dornase alfa. Both are identified as relatively burdensome, are intended to improve mucociliary clearance and have demonstrated dynamic effects on measures of pulmonary function (5-8). Early studies with either hypertonic saline or dornase alfa demonstrated a return to baseline lung function (i.e., pre-treatment FEV₁ % predicted) within 14 days of stopping the treatment (6). HEMT (i.e., ivacaftor) also improves lung function and mucociliary clearance, with demonstrably greater effects than either hypertonic saline or dornase alfa (1, 2, 7). Data indicate that ETI may be even more effective than ivacaftor monotherapy at improving CFTR function and airway clearance, and ETI will be indicated for a much larger proportion of people with CF. It is not known if hypertonic saline or dornase alfa improve or maintain pulmonary health above what is already gained through ETI use.

FEV₁ % predicted has been the most frequently used outcome measure of lung function in CF clinical trials, including studies of hypertonic saline, dornase alfa, and HEMT (2, 6, 8, 9). However, an alternative

and perhaps more sensitive measure of change in lung function using multiple breath washout (MBW) and the lung clearance index (LCI) has also been used to test pulmonary benefits from muco-active drugs or modulators (7, 10, 11). LCI improvement from ivacaftor in those with G551D was nearly twice the effect measured with either inhaled hypertonic saline or dornase alfa, though study population demographics differed (7, 10, 11). LCI is more useful in those with better preserved lung function and it is unclear how it will perform in the group recruited to SIMPLIFY. LCI is also not available at all study sites. However, the potential to capture even small changes in pulmonary function through LCI, possibly in those with higher baseline lung function, is valuable and LCI will be conducted at SIMPLIFY sites with this capability as a secondary outcome measure.

Including spirometry and LCI may increase the ability of this master protocol to detect and understand the impact of treatment withdrawal on airway function. Additionally, mucociliary clearance (MCC) scans will be done at a small number of SIMPLIFY study sites with this capability and may provide important physiological data related to spirometry and MBW (12). Consistency across all three of these related outcome measures would increase confidence in the interpretation of the trial results. If this master protocol determines that people on ETI who discontinue these therapies have no appreciable loss in lung function or change in MCC, our hypothesis will be supported that certain daily therapies might not be necessary or beneficial in at least some people treated with ETI. If this master protocol demonstrates that people treated with ETI who continue hypertonic saline or dornase alfa have measurably better outcomes, then these data will help to justify the time, effort and cost of continuing such treatments.

Transformative improvement in CF clinical care through HEMT represents an important opportunity to test the impact of withdrawing chronic therapies, specifically hypertonic saline and dornase alfa, in a randomized, controlled setting. Observational studies of treatment withdrawal are prone to confounding by indication and, if insufficiently powered, may be difficult to interpret. SIMPLIFY will limit indication bias through randomization and is powered to test hypotheses of non-inferiority in order to determine whether discontinuation of each therapy is comparable to continuing therapy as measured by change in pulmonary function. As there are currently no data from controlled trials testing the effects of discontinuing these therapies in CF, the results of this protocol will be important when considering individual treatment decisions among the increasingly large percentage of people with CF on highly effective modulator therapies.

2.1 Risk / Benefit Assessment

Drug Intervention: Each study in this master protocol is unblinded and there is no study drug or new exposure to a drug compound. Subjects enrolled in a study will be randomized to either continue or discontinue a medication that has already been clinically prescribed and used prior to enrollment. It is possible that discontinuing a medication (i.e., hypertonic saline or dornase alfa) will result in a decline in health. Determining whether or not this occurs among people on chronic ETI is the purpose of the protocol and subjects will be monitored closely. The length of each study has been minimized to an interval that is thought to be sufficient to determine if a change in lung function occurs. After the 6-week randomized participation period to either Study A (hypertonic saline) or Study B (dornase alfa), subjects and their care providers will decide whether or not to continue use of these medications. Subjects who experience an adverse event (AE) during Study A or Study B should be treated by clinical indication, including the potential to restart any medication that was stopped for this study.

Spirometry Test: Potential shortness of breath or light headedness.

MBW Test: The instrument to be used for the MBW test is the Exhalyzer® D by Eco Medics AG (Duernten, Switzerland). There is a very small risk of hyperventilation, which is minimized because each

breath will be visualized on the computer screen in real time and the exhaled gases are monitored. Rarely with hyperventilation, there may be dizziness or fainting.

MCC Test: The following complications could result from inhalation of nebulized aerosols: cough, shortness of breath, hoarseness, throat irritation, temporary decrease in lung function measurements, wheezing and decrease in oxygen saturation. The MCC procedure entails exposure to some radiation. The amount of radiation dose received during a given study (2 MCC scans) is approximately 0.9 mSv. The risk from the radiation dose received from this procedure is too small to be detected but is significantly less than the radiation dose received from the natural environment over the course of 1 year (3 mSv). Since radiation risk is a cumulative risk concern, an eligibility criterion has been added to exclude patients whose recent radiation exposure is greater than typical. Typically, significant additional radiation exposure in CF patients (above environmental exposure) would come from chest computed tomography (CT) procedures. Patients who have had more than 2 chest CTs in the past year or a combination of procedures that are believed to have exposed the subject's lungs to >150 mSv for adults ≥ 18 years old, >15 mSv for children < 18 years would be excluded. In addition, a potential risk of radiation exposure to an unborn fetus exists among pregnant females. All those able to become pregnant will be required to undergo a pregnancy test.

3 STUDY DESIGN

3.1 Study Overview

This is a master protocol with two concurrent randomized trials. It is designed to evaluate the independent effects of discontinuing hypertonic saline (Study A) and dornase alfa (Study B) in people with CF age 12 and older taking ETI for at least 90 days prior to study screening. Individuals with CF ages 12-17 years with FEV₁ 70% predicted or greater and those 18 years and older with FEV₁ 60% predicted or greater may enroll. There is no upper limit for FEV₁% predicted. Study A and Study B are identical randomized, open label two-arm randomized trials consisting of a 2-week screening period, randomization to continue or discontinue hypertonic saline (Study A) or dornase alfa (Study B), followed by a 6-week study period. Only those that remain clinically stable and maintain adequate reported adherence to inhaled drug therapy between screening and Visit 1 will be eligible for randomization.

Subjects currently being treated with only hypertonic saline or dornase alfa will be enrolled in Study A or Study B (as applicable) and will be randomized 1:1 to either continue or discontinue their current prescribed therapy.

Subjects who are currently being treated with both hypertonic saline and dornase alfa will remain on both therapies during the screening period and then be randomized to Study A (hypertonic saline) or Study B (dornase alfa) as well as randomized (1:1) to continue or discontinue the applicable therapy. The randomization to Study A or Study B among subjects on both therapies is not optional and is essential to reduce indication bias and ensure comparable populations across studies. After completion of the first study, these subjects may subsequently enroll in the alternate study if they meet eligibility criteria.

For subjects randomly assigned to continue their therapy during a given study, this therapy should be taken at least once daily according to each subject's pre-existing, clinically prescribed regimen (e.g., daily, twice daily). The concentration of hypertonic saline will also be according to clinical prescription (e.g., 7% sodium chloride or 3.5% sodium chloride). Hypertonic saline concentration must be at least 3%.

[figure not shown]
Clinical outcomes (FEV₁, antibiotic use, pulmonary exacerbations, and patient reported outcomes), safety (AEs), and subject perception of how stopping HS or dornase alfa (or both) would impact their daily life will be evaluated at all sites during each study. Additional measurements will be conducted at selected study sites with the capabilities to conduct these procedures:

- MBW to evaluate changes in LCI
- MCC scans using inhaled radio-labeled particles and imaging techniques to evaluate changes in mucociliary clearance

Each study includes four study visits over a period of 8 weeks, including the 2-week screening period.

- Subjects taking only hypertonic saline or only dornase alfa upon study entry at the Screening Visit would participate in study visits for up to 8 weeks.
- For subjects taking both hypertonic saline and dornase alfa upon study entry at the Screening Visit:
 - They have the potential to participate in either one or both studies. Subjects would participate in the first study for up to 8 weeks. After completion of the last visit in the first study, subjects may consider enrollment into the second study. If subjects are eligible and enroll in the second study, they would participate in study visits for up to an additional 8 weeks.
 - Participation in the two studies may be consecutive or separated by any length of time.
- All subjects will additionally be asked to complete electronic questionnaires approximately every 28 days for up to 24 weeks after their final study visit (Visit 3, Week 6). For subjects who participate in a second study within 24 weeks of completing the first, the post study questionnaires from the first study may be stopped.

A data monitoring committee (DMC) will be reviewing safety data on an ongoing basis for both studies. Upon interim review of safety data, an optional cohort with lower baseline lung function may be enrolled into Study A (hypertonic saline). The optional cohort will include people with CF \geq 18 years old with FEV₁ between 40 and less than 60 % predicted who satisfy the remaining criteria for participation in Study A. Additional endpoints, including LCI and MCC, will not be obtained in this cohort.

4 STUDY OBJECTIVES

4.1 Primary Objective

The primary objectives are:

Study A: To determine whether discontinuing hypertonic saline is non-inferior to continuing hypertonic saline among people with CF on ETI, as measured by the 6-week absolute change in FEV₁ % predicted.

Study B: To determine whether discontinuing dornase alfa is non-inferior to continuing dornase alfa among people with CF on ETI, as measured by the 6-week absolute change in FEV₁ % predicted.

4.2 Secondary Objectives

The secondary objectives of each study are to evaluate:

- The safety of discontinuing vs. continuing hypertonic saline (Study A) or dornase alfa (Study B)
- The effect of discontinuing vs. continuing hypertonic saline (Study A) or dornase alfa (Study B) on lung clearance index (LCI)

- The effect of discontinuing vs. continuing hypertonic saline (Study A) or dornase alfa (Study B) on other clinical outcomes (e.g., antibiotic events, pulmonary exacerbations, and patient reported outcomes)

4.3 Exploratory Objectives

The exploratory objectives of this study are to:

- Evaluate the effects of discontinuing vs. continuing hypertonic saline (Study A) or dornase alfa (Study B) on mucociliary clearance (MCC)
- To estimate and compare the effects of discontinuing vs. continuing both hypertonic saline and dornase alfa among the subgroup of subjects using both chronic therapies
- Among those enrolled in a lower lung function cohort, evaluate the effects of discontinuing vs. continuing hypertonic saline (Study A) on safety and clinical endpoints
- Evaluate hypertonic saline and/or dornase alfa use up to 24 weeks after completion of each study and associate the decision to remain on or off therapy after the study with both randomization assignment and study outcomes
- Evaluate self-reported acute antibiotic use up to 24 weeks after completion of each study, comparing those who choose to use vs. not use inhaled hypertonic saline or dornase alfa
- Evaluate subject perception of how stopping HS or dornase alfa (or both) would impact their daily life

5 STUDY ENDPOINTS

5.1 Primary Endpoint

The primary endpoint in each study is the absolute change in FEV₁ % predicted from Visit 1 (randomization) to Visit 3 (week 6).

5.2 Secondary Endpoints

Secondary endpoints in each study include:

Efficacy

- Change in LCI from Visit 1 (randomization) to Visit 3 (week 6)
- Change in FEV₁ % predicted from Visit 1 (randomization) to Visit 2 (week 2)
- Proportion of subjects initiating acute antibiotics from Visit 1 (randomization) to Visit 3 (week 6)
- Proportion of subjects hospitalized from Visit 1 (randomization) to Visit 3 (week 6)
- Proportion of subjects with a pulmonary exacerbation from Visit 1 (randomization) to Visit 3 (week 6)
- Change in Chronic Respiratory Infection Symptom Score (CRISS) from Visit 1 (randomization) to Visit 3 (week 6)

- Change in the Cystic Fibrosis Questionnaire-Revised (CFQR) Respiratory Domain from Visit 1 (randomization) to Visit 3 (week 6)
- Change in FEV₁ % predicted from Screening to Visit 1 (randomization)

Safety

- Incidence of adverse events occurring between Visit 1 (randomization) to Visit 3 (week 6)
- Proportion of subjects temporarily or permanently changing their assigned therapy regimen between Visit 1 (randomization) to Visit 3 (week 6)

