7.1 Required Medications and Treatments

For each study:

- Subjects must continue ETI from Screening to Visit 3 (week 6).
- Subjects must continue hypertonic saline and/or dornase alfa (as applicable to Study A or Study B) from Screening to Visit 1 (randomization).

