8 STUDY TREATMENTS

8.1 Method of Assigning Subjects to Studies and Treatment Groups

At the randomization visit (Visit 1), those subjects who are eligible and taking only either hypertonic saline or dornase alfa will be enrolled in the appropriate study (A or B). If both studies remain open to enrollment, those taking both and enrolling for the first time will be randomized to study (A or B). If only one study is open for enrollment, eligible subjects taking both therapies may be enrolled into only the open study. Those taking both and who are eligible and enrolling for the second time may enroll in the study that they were not previously in if that study remains open for enrollment.

At Visit 1, subjects will be randomized 1:1 to continue or discontinue the applicable therapy. Randomization will occur by a predetermined scheme using block randomization with the goal of ensuring balance between treatment arms as detailed in the Statistical Analysis Plan (SAP). Within each study, randomization will be stratified by Visit 1 FEV₁ % predicted ($\geq 90\%$, $< 90\%$), treatment combination at screening (single or concurrent use of hypertonic saline and/or dornase alfa), prior study participation (yes/no), and age (≥ 18 vs < 18). Subjects enrolled in the lower lung function cohort will be similarly randomized to continue or discontinue hypertonic saline and stratified by current dornase alfa use. Any deviations from the randomization schema will be documented in the SAP.

Randomization will occur centrally using a web-based randomization system linked to the electronic data capture (EDC) system. Only authorized site personnel are given access to the randomization module in EDC. Authorized site personnel will enter subject eligibility information and whether or not the subject signed informed consent. If the information entered into the EDC system is consistent with eligibility criteria for the study, the system will provide the appropriate authorized site personnel with a randomization assignment for that subject that matches a specific treatment arm.

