14.3 Analysis of Secondary Endpoints

Differences between treatment arms will be estimated within each study for i) subjects initiating acute antibiotics, ii) subjects hospitalized, iii) subjects with a pulmonary exacerbation, and iv) subjects who meet adherence criteria. These differences will be estimated using logistic regression methods and reported with confidence intervals accounting for randomization strata.

Differences in the between treatment arms from randomization to week 6 will be estimated in each trial for i) CRISS, ii) CFQR, and iii) LCI using general linear regression adjusting for randomization strata. Change in FEV₁ % predicted from Screening to randomization will also be compared between treatment arms within each study using linear regression adjusting for randomization strata. Descriptive summaries of the change from Screening to randomization, and randomization to week 2 will also be provided for all continuous endpoints.

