This table summarizes the FEV₁ (L) results at Week -2 (Screening), Week 0 (Randomization), Week 2 (Visit 2), and Week 6 (Visit 3). Changes from are also given with reference visit as indicated (either Week -2 or Week 0). Relative change is calculated as 100 * (post visit value – reference value) / (reference value)

Visit	Statistic	STOP Taking (N=)	KEEP Taking (N=)	Difference (95% CI)[1]	P-value[1] [Final Report only]
Week -2 (Screening)	N(%) Mean (SD) Median Min, Max				
Week 0 (Randomization)	N(%) Mean (SD) Median Min, Max				
Absolute Change (Week -2 to Week 0)	N(%) Mean (SD) Median Min, Max				
Relative Change (Week -2 to Week 0)	N(%) Mean (SD) Median Min, Max				
Week 2 (Visit 2)	N(%) Mean (SD) Median Min, Max				
Absolute Change (Week 0 to Week 2)	N(%) Mean (SD) Median Min, Max				
Relative Change (Week 0 to Week 2)	N(%) Mean (SD) Median Min, Max				
Difference in Absolute Changes (Week 0 to Week 2 minus Week -2 to Week 0)	N(%) Mean (SD) Median Min, Max				
Week 6 (Visit 3)	N(%) Mean (SD) Median Min, Max				

Absolute Change (Week 0 to Week 6)	N(%) Mean (SD) Median Min, Max				
Relative Change (Week 0 to Week 6)	N(%) Mean (SD) Median Min, Max				

[1] 95% confidence interval and p-value are calculated using a two-sample t-test. The difference is STOP Taking – KEEP Taking.

Table 7.4. Results from ANOVA Model for Change in FEV₁ (% Predicted) During the Run-In Period (PPA population Final Report Only)

Absolute change in FEV₁ (% Predicted) from Week -2 to Week 0, is compared between intervention arms using Analysis of Variance adjusted for dichotomous randomization strata: Week 0 FEV₁, treatment combination at screening, prior study enrollment, and Week 0 age. An unadjusted estimate is also provided.

Model Covariates	STOP Taking Mean Estimate (N=)	KEEP Taking Mean Estimate (N=)	Δ FEV ₁ (% Predicted) Estimate (95% CI)	P-value [8]
Model Unadjusted				
Intervention Arm:	STOP Taking hypertonic saline [1,2]			
Model Adjusted for Randomization Strata				
Intervention Arm:	STOP Taking hypertonic saline [2,3]			
Randomization Strata:	FEV ₁ % Predicted ≥90% [4] On both HS and Dnase [5] Prior study enrollment [6] Age ≥18 years [7]			

- [1] The overall unadjusted intervention arm difference (STOP Taking - Keep Taking) is estimated using a two sample t-test.
- [2] Compared to reference level, KEEP taking hypertonic saline.
- [3] Least Square Means Estimates from model.
- [4] Compared to reference level, FEV₁ % Predicted < 90% at Week 0 (Visit 1).

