- [5] Compared to reference level, one therapy at Week -2 (Screening).
- [6] Compared to reference level, no prior study enrollment.
- [7] Compared to reference level, age <18 years at Week 0 (Visit 1).
- [8] Two-sided test of null hypothesis of no difference

8 Exacerbation and Concomitant Medication Parameters

Table 8.1. Distribution of Antibiotic Use and Protocol-Defined Pulmonary Exacerbations (ITT population)

This table displays the distribution of protocol-defined pulmonary exacerbations (PEX) experienced by the participants from Week 0 (Visit 1) to Week 6 (Visit 3).

	STOP Taking (N=)	KEEP Taking (N=)	Difference (95% CI)	p-value [Final Report Only]
Total Number of Pulmonary Exacerbations [1] Rate of PEX per week of follow-up [2] Average number of PEX per participant			Rate Ratio (95% CI) [5]	p-value[5]
Distribution of Exacerbations, n (%) [1] 0 1 2				
Total no. patients with at least one Pulmonary Exacerbation, n (%)			Difference (95% CI) [6]	p-value[7]
Requiring IV Abx, n (%) [3] Requiring Oral Abx, n (%) [3, 4] Requiring Inhaled Abx, n (%) [3] Requiring Hospitalization, n (%) [3]				

[1] Protocol-Defined PEX. Exacerbations are counted as unique if their first prescription dates occur greater than 20 days apart. Protocol-defined PEX is determined by using Fuchs criteria]: clinical need for antibiotics as indicated by presence of at least 4 of 12 possible signs or symptoms listed below:

- Change in sputum volume or color
- New or increased hemoptysis
- Increased cough
- Increased dyspnea
- Increased malaise, fatigue or lethargy
- Temperature over 38°C
- Anorexia or weight loss
- Sinus pain or tenderness
- Change in sinus discharge
- Change in physical findings on examination of the chest
- Decrease in pulmonary function by 10% or more
- Radiographic changes.

[2] The total number of follow-up weeks in the STOP Taking group is X and in the KEEP Taking group is X.

[3] Percentages are based on total number of patients with at least one pulmonary exacerbation.

[4] Includes g-tube.

[5] Quasi-Poisson regression is used to calculate the rate ratio, 95% CI and corresponding p-values. The ratio is STOP Taking / KEEP Taking.

[6] The 95% confidence interval for difference in proportions is calculated using the Newcombe-Wilson method without continuity correction. The difference is STOP Taking – KEEP Taking.

[7] The p-value is based on the Fisher Exact test. Included in Final Report only.

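### A secondary efficacy endpoint that ends at randomization is tested between arms, while the Week 2 FEV₁ change has no strata-adjusted model

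*Protocol*

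**What the plan says.** **Endpoints.** The efficacy list in Protocol 5.2 contains two short-interval FEV₁ changes. One runs forward from randomization: "Change in FEV₁ % predicted from Visit 1 (randomization) to Visit 2 (week 2". The other runs up to it: "Change in FEV₁ % predicted from Screening to Visit 1 (randomization".

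**Timing.** Protocol 7.1 states: "Subjects must continue hypertonic saline and/or dornase alfa (as applicable to Study A or Study B) from Screening to Visit 1 (randomization". Protocol 6.3.2 excludes, before randomization, anyone whose FEV₁ % predicted has fallen by 10 points or more since Screening. Protocol 8.1 adds that "randomization will be stratified by Visit 1 FEV₁ % predicted".

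**Analysis of the run-in change.** Protocol 14.3 says that it "will also be compared between treatment arms within each study using linear regression adjusting for randomization strata". SAP 3.2.7 repeats this. In SAP Table 7.4 the change "from Week -2 to Week 0, is compared between intervention arms using Analysis of Variance adjusted for dichotomous randomization strata", and footnote 8 describes the p-value as "Two-sided test of null hypothesis of no difference". Table 7.4 is specified for the PPA population only.

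**Analysis of the Week 2 change.** Protocol 14.3 offers no model: "Descriptive summaries of the change from Screening to randomization, and randomization to week 2 will also be provided" for the continuous endpoints. SAP 3.2.7 promises mean differences with 95% intervals at each visit, but names a t-test only for Week 0 to Week 6. SAP Table 7.1, planned in both ITT and PPA, has a Week 0 to Week 2 row and a Week -2 to Week 0 row. Both sit under columns for the unadjusted difference, 95% CI and t-test p-value. Table 7.3 repeats the layout in liters.

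**The concern.** An efficacy endpoint should be able to respond to the intervention. The run-in change cannot, because no arm exists while it accrues. A p-value for it, placed among the efficacy endpoints, invites a reading that the data cannot bear.

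The choice of population adds to this. PPA membership (SAP 2.4) depends on diary completion, adherence to the assigned arm, antibiotic starts and a non-missing Week 6 FEV₁, all observed after randomization. If those filters act differently in the two arms, the retained groups may differ in run-in change although the randomized groups did not. Protocol 14.1.1 assigns secondary summaries to ITT, and SAP 2.4 says that secondary analyses are run on PPA and repeated on ITT. Yet no ITT version of the adjusted run-in model is laid out.

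The allocation of models is also the wrong way round. The four stratification factors are used for the FEV₁ secondary endpoint that cannot show an effect of stopping therapy, and not for the one that can.

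**Working it through.** **1. Is the change fixed before allocation?** Visit 1 FEV₁ is needed to apply the 10-point criterion (Protocol 6.3.2) and to select the randomization stratum (8.1). Both steps come before assignment, and all subjects stay on therapy until then (7.1). Both ends of the interval are therefore known before any arm exists. Among all randomized subjects the expected between-arm difference is zero, whatever discontinuation does later.

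**2. The plan's own power figure.** Inputs from Protocol 14.7 and 14.2: 308 evaluable (154 per arm), SD 8.4, margin 3, one-sided alpha 0.025.
- SE = 8.4 × √(2/154) = 0.957.
- True difference 0: Φ(3/0.957 − 1.96) = 0.880, against a stated 88%.
- True difference −0.5: Φ(2.5/0.957 − 1.96) = 0.743, against a stated 74%.

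Both reproduce. The sample size is not in question.

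**3. What each test can see.** The documents give no SD for the run-in or the Week 2 change. I assume the 6-week value, 8.4, for both, with 200 per arm, two-sided 0.05 and 4,000 simulated trials per effect. The Week 2 column is the analytic power; the simulated rates agree.

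| True effect of discontinuation | Run-in test rejects | Week 2 test rejects |
|---|---|---|
| 0 | 4.8% | 5% |
| −1.5 | 5.3% | 43% |
| −3 | 5.0% | 95% |
| −5 | 4.8% | >99.9% |

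The run-in column stays at alpha by construction, because the effect cannot enter a change that ends before allocation. The table illustrates step 1 and is not separate evidence for it.

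**4. What adjustment would add at Week 2.** Half-width of the 95% CI = 1.96 × SD × √(1 − R²) × √(2/n per arm), where R² is the assumed share of variance explained by the strata.

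| n per arm | SD | R² = 0 | 5% | 10% | 20% |
|---|---|---|---|---|---|
| 200 | 8.4 | 1.65 | 1.60 | 1.56 | 1.47 |
| 200 | 6 (assumed) | 1.18 | 1.15 | 1.12 | 1.05 |
| 154 | 8.4 | 1.88 | 1.83 | 1.78 | 1.68 |

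**5. Where adjusted FEV₁ models exist.** SAP Tables 6.1.a, 6.1.b and 6.2 cover Week 6, and Table 7.4 covers the run-in. None covers Week 2.

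**The case against.** The strongest reply is that little depends on this. Table 7.4 is titled as a run-in analysis and sits with the spirometry results, so an attentive reader would take it as a pre-randomization check. No decision uses its p-value: neither the non-inferiority test nor the excess-harm boundary draws on it. That stands and limits the severity. It does not remove the point, because Protocol 5.2 calls the change an efficacy endpoint and neither document describes the comparison as a balance check.

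Week 2 is also better served than the lack of an adjusted model suggests. A reader might infer that it has no between-arm comparison, but Table 7.1 gives one in ITT and PPA. Figure 7.1 plots the change in both populations, and Table 5.3 compares the proportions with declines of at least 5 and at least 10 points at Week 2 in ITT. The unadjusted ITT difference is a valid estimate. What is missing is precision and consistency with the other models.

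A reader might also think that the 10-point exclusion, or adjustment for the Week 0 FEV₁ stratum, biases the run-in contrast. Both are fixed before randomization and apply alike to the future arms. The exclusion narrows the distribution, and the stratum term makes its own coefficient hard to interpret. Neither distorts the arm coefficient in the randomized population.

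**Conclusion.** The point holds as a minor one. The Screening to Visit 1 change does not belong among the efficacy endpoints, and its between-arm test tells nothing about discontinuation. The Week 2 change is a named secondary endpoint that can respond, and it lacks the strata-adjusted model. The gain from adding that model is modest, at roughly 0.05 to 0.18 points of half-width (1.65 − 1.60 and 1.65 − 1.47) at 200 per arm. This rests on the assumed SD of 8.4 and on strata explaining 5–20% of variance.

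Two stronger readings are not supported:

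- A false-positive rate of 5% per study, or 1 − 0.95² = 9.75% over both studies, might be attached to Table 7.4. Those rates belong to a test in the full randomized population, and the second also needs independent studies. Table 7.4 is PPA-only, where the null is not guaranteed, and Protocol 6.1 expects some people to enroll in both studies.
- Protocol 2 reports a return to pre-treatment lung function within 14 days in early studies of these drugs, which might be read as making Week 2 the expected time of loss here. The same section says it is unknown whether either therapy adds anything beyond ETI, and the plan makes Week 6 primary.

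**What to change.** 1. Move the Screening to Visit 1 change out of the efficacy list in Protocol 5.2 and report it descriptively, by arm and overall, as a run-in summary.
2. Remove its between-arm test from Protocol 14.3, SAP 3.2.7 and SAP Table 7.4.
3. Remove the p-values from the Week -2 to Week 0 rows of SAP Tables 7.1 and 7.3. Otherwise the same comparison survives there. The rows that subtract the run-in change from the Week 0 to Week 2 change can stay, since they include follow-up after randomization.
4. Apply the existing strata-adjusted ANOVA to the Week 0 to Week 2 change in FEV₁ % predicted, in ITT and PPA. State this in Protocol 14.3 and SAP 3.2.7 so that the text and the table shells agree.

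The cost is wording in both documents and one table redirected to a different interval. No new data are needed, and the only loss is a baseline-balance p-value.
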